## 12.2 Secondary Objectives

- Secondary and exploratory objectives: We will compare antibody levels in autologous vs. allogeneic transplant, cord vs. non-cord allogeneic transplant, matched vs. mismatched transplants, in patients with and without GVHD, and in patients with and without diarrhea to test if HLA-mismatching, GVHD, and/or diarrhea are associated with accelerated antibody decay. Diarrhea will be assessed on the weekly questionnaire and the presence/severity/tissue involvement of GVHD will be assessed by review of the medical record at all timepoints indicated in Figure 1. We will also compare antibody levels from serum collected by venipuncture versus self-collected using a TASSO device and from fluid collected by nasal swabs. Based on preliminary and published data, we expect a high concordance between antibody levels from capillary blood collected by TASSO and venous blood collected by venipuncture or from a central venous catheter. If there is a slight discrepancy, we can calculate a correction factor based on the results from the paired specimens collected on week 12. If there is an unexpected significant discrepancy between antibody levels that cannot be corrected, we will have a venous blood draw at week 24 to calculate half-life using just venous blood samples. We will monitor for breakthrough SARS-CoV-2 infection by PCR of fluid collected by nasal swabs. If breakthrough infection does occur, we may sequence the spike gene (or entire viral genome) to determine the variant and identify possible resistance mutations. We will also measure anti-drug antibodies in case this is correlated with half-life. We will also monitor routine safety labs as part of standard post-transplant care. Comparisons will be tested using a t-test. As part of an exploratory analysis, we may also calculate the half-life of VIR-7831 and of SARS-CoV-2 neutralizing antibodies in nasal swabs and of SARS-CoV-2 neutralizing antibodies in serum after infusion of VIR-7831.

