### **3. STUDY OBJECTIVES**

#### **3.1 Primary Objective**

To determine the levels of VIR-7831 mAb post-transplant in serum over time.

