#### **3.2 Secondary Objectives**

1. To compare the half-life of VIR-7831 in autologous vs. allogeneic transplant, cord vs. non-cord allogeneic transplant, matched vs mis-matched donors, in patients with and without GVHD, and in patients with and without diarrhea

2. To monitor the frequency of breakthrough SARS-CoV-2 acquisition in HCT recipients who have received VIR-7831
3. To compare antibody levels from serum collected by venipuncture versus self-collected using a TASSO device.
4. To monitor the development of anti-drug antibodies
5. To monitor safety
6. Exploratory: To measure VIR-7831 and SARS-CoV-2 neutralizing antibodies in nasal swabs and SARS-CoV-2 neutralizing antibodies in serum.

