#### 12.1.1 Pharmacokinetics Assessment

- Primary objective: To determine the levels of VIR-7831 mAb post-transplant in serum over time. Both compartmental and non-compartmental analyses are used to assess pharmacokinetic parameters. The half-life of the anti-SARS-CoV-2 monoclonal antibody and neutralizing antibody titers in the serum will be calculated by a one-phase exponential decay model. We will compare fold-changes in antibody levels by normalizing to pre-transplant levels for each subject. Levels of VIR-7831 can be measured using an idiotypic antibody assay that is not affected by COVID-19 infection or vaccination. In addition, to half-life, we will calculate  $C_{max}$ ,  $T_{max}$ , AUC from the concentration over time plots.

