## 12.3 Sample Size and Accrual

At the Fred Hutch, we perform approximately 250 allogeneic transplants per year, approximately 5% of which involve umbilical cord blood donors. We also perform approximately 180 autologous transplants per year. The target enrollment for this trial is approximately 50 HCT candidates, of which ten participants will be autologous HCT candidates and 40 will be allogeneic HCT candidates (including cord blood HCT candidates). At least 8 of the allogeneic HCT candidates will be from HLA-mismatched (related or unrelated) HCT recipients. Based on the estimated number of treated patients per year (and previously treated patients since 2013), as well as the estimated number of patients that we may enroll (i.e., ‘feasible’ patients) after accounting for estimated eligibility and consent rates, it will be feasible to enroll approximately 55 subjects over 6-12 months. Our final estimated sample size will be 50 subjects after accounting for an estimated 10% dropout prior to completion of the full 24-week study period. If the dropout rate is higher at three months after mAb infusion, we may enroll more patients to achieve a target of 50 overall subjects. The study is open to anyone regardless of gender or ethnicity. Efforts will be made to extend the accrual to a representative population. If accrual is slow, we may add another site. If accrual of the HLA-mismatched strata is slow, we may analyze and report the results in the HLA-matched strata once that is fully enrolled given the urgency of the pandemic.

- Primary objective: Our primary endpoint is to calculate the half-life of VIR-7831 post-transplant. Based on the half-life seen with other antibodies containing the LS mutation in adults who have not undergone transplant, we anticipate a half-life of up to 3 months. However, this half-life may be shortened in transplant recipients. Since we will use descriptive statistics, the sample size is

sufficient to provide data to calculate the half-life. Levels of VIR-7831 can be measured using an idiotypic antibody assay that is not affected by COVID-19 infection or vaccination.

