- Secondary and exploratory objectives: We anticipate enrolling ten autologous HCT candidates. We anticipate enrolling approximately eight HCT candidates receiving HLA-mismatched (related or unrelated) transplants. This will serve as pilot data to examine whether HLA-mismatch affects the half-life of VIR-7831. To compare antibody levels between venipuncture vs TASSO and nasal swab in the first month of the study, we will have at least  $4 \times 50 = 200$  specimens in each group. Based on the phase 3 COMET-ICE study, we do not anticipate any adverse effects or safety signals. Although there is currently no data available on the use of VIR-7831 as prophylaxis, it is possible we may observe breakthrough infection with SARS-CoV-2, particularly towards the end of the study as antibody levels wane.

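### Section 12.2 gives antibody levels, not half-life, as the variable for the transplant-group t-tests, and section 12 does not say how the 500 mg and 2,000 mg subjects are handled when levels, Cmax or AUC are reported

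*Combined protocol and SAP*

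**What the plan says.** **Objectives.** The primary objective (section 3.1) is "To determine the levels of VIR-7831 mAb post-transplant in serum over time". Secondary objective 1 (section 3.2) begins "To compare the half-life of VIR-7831 in autologous vs. allogeneic transplant" and goes on to cord vs non-cord, matched vs mismatched, GVHD and diarrhea.

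**Analysis text.** For those same contrasts section 12.2 says "We will compare antibody levels in autologous vs. allogeneic transplant, cord vs. non-cord allogeneic transplant, matched vs. mismatched transplants". It gives the purpose as learning whether HLA-mismatching, GVHD or diarrhea "are associated with accelerated antibody decay", and adds "Comparisons will be tested using a t-test". It states no time point, scale or summary measure.

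**Elsewhere in section 12.** Section 12.3 says "Our primary endpoint is to calculate the half-life of VIR-7831 post-transplant" and, of the mismatched group, "This will serve as pilot data to examine whether HLA-mismatch affects the half-life of VIR-7831". Section 12.1.1 plans a one-phase decay fit, Cmax, Tmax and AUC, and says "We will compare fold-changes in antibody levels by normalizing to pre-transplant levels for each subject". It does not name the reference sample.

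**Dose.** The Synopsis (Statistical Methods) and section 4 give 20 subjects already infused at 500 mg and 30 to be infused at 2,000 mg. Section 7 expects exposure to scale with dose between the two, and says that no PK data are yet available at 2,000 mg. Section 12 does not mention dose.

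**The concern.** There are two linked gaps. First, the variable in the analysis text (levels) differs from the variable in the objective (half-life). Second, a level depends directly on dose and a half-life should not, so the choice matters in a study with a four-fold dose change part-way through.

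An analyst who took 12.2 at its word, on levels from all 50 subjects with no allowance for dose, would add a large between-dose spread to every group comparison and could miss real differences. For the primary objective, one concentration curve, Cmax or AUC summarised over both doses would describe neither dose group.

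**Working it through.** **Inputs.** Doses: 20 at 500 mg, 30 at 2,000 mg (section 4). Groups: 10 autologous, 40 allogeneic (section 12.3). Both splits total 50. Predicted week-12 level at 2,000 mg: median 84.3 µg/mL, 10th to 90th percentile 52.8 to 126.7 (section 1; a population PK model built on studies that were not in transplant recipients). Dose proportionality: section 7. The plan states no power, alpha or effect size for the t-tests, so there is no power figure to reproduce. I assume two-sided 0.05 and a 1.5-fold difference.

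**Spread.**
- Within one dose: log SD = ln(126.7/52.8)/(2 × 1.2816) = 0.3415; variance 0.1166.
- Between doses: 0.4 × 0.6 × (ln 4)² = 0.461.
- Both doses together: √(0.1166 + 0.461) = √0.578 = 0.760. Dose makes up 0.461/0.578 = 80% of the variance.

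**Descriptive summary at week 12.**
- Under proportionality the 500 mg values are 84.3/4 = 21.1, with 10th to 90th percentile 52.8/4 = 13.2 to 126.7/4 = 31.7.
- The geometric mean over both doses is 84.3 × 4^(−0.4) = 48.4. That lies above the 500 mg range (13.2 to 31.7) and below the 2,000 mg range (52.8 to 126.7).
- The simulated 20:30 mixture has a 10th to 90th range of 16.7 to 117.2, a ratio of 7.0. At one dose the ratio is 126.7/52.8 = 2.4.

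**Power if unadjusted levels were tested** (Student t-test on log levels, 10 vs 40, ratio 1.5, 20 of the 50 on 500 mg). The average is over the number k of the 10 autologous subjects on 500 mg, weighted by the hypergeometric distribution.

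| Log SD within dose | One dose | Both doses, averaged | Both doses, balanced (k = 4) |
|---|---|---|---|
| 0.25 (assumed) | 99% | 33% | 10% |
| 0.34 (section 1) | 91% | 31% | 13% |
| 0.50 (assumed) | 61% | 26% | 14% |
| 0.70 (assumed) | 36% | 21% | 13% |

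At log SD 0.34, a dose term in the model restores power to 90–91%.

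**False positives** (log scale, SD 0.34, no true difference). The spurious autologous/allogeneic ratio is 4^((20−k)/40 − k/10).

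| k of 10 on 500 mg | Chance of this split | Spurious ratio | Rejection rate |
|---|---|---|---|
| 0 | 0.3% | 2.00 | 93% |
| 1 | 2.8% | 1.68 | 47% |
| 2 | 10.8% | 1.41 | 6% |
| 4 | 28.0% | 1.00 | 0% |
| 6 | 10.3% | 0.71 | 6% |
| 7 | 3.1% | 0.59 | 48% |
| 8 | 0.5% | 0.50 | 93% |

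Averaged over all splits, the rate is 5.0%.

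**Half-life.** One-phase fits to the same two-phase curve at 1× and 4× dose gave identical half-lives at each dose, for assumed terminal values of 10, 21, 58 and 90 days. If proportionality failed, so that half-life at 2,000 mg were g times that at 500 mg, the autologous/allogeneic ratio would shift by g^((20−k)/40 − k/10). For g = 0.8 (assumed), k = 2 gives 0.8^0.25 = 0.95 and k = 8 gives 0.8^(−0.5) = 1.12.

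**The case against.** The strongest reply is that the plan does not intend a test of raw levels. Objective 1, the primary endpoint in 12.3, the mismatch aim in 12.3 and the end of the 12.2 sentence itself all concern decay. Section 12.1.1 also supplies a measure that cancels dose: a fold-change per subject from a pre-transplant value. Infusion precedes conditioning by at least 24 hours, so a sample can be both post-infusion and pre-transplant. For the drug that is the only sensible reference, because a pre-infusion sample contains none. Much of this stands, and half-life or fold-change is the likelier reading. But 12.1.1 does not name the sample, 12.2 does not say that its tests use the fold-change, and a fold-change does not cover Cmax or AUC.

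A second reply is that pooling is nowhere stated. That is correct. A reader might infer from the silence that one curve over both doses is planned. The documents do not support that: both doses and the 20/30 split are explicit in the Synopsis and section 4, the compartmental analysis in 12.1.1 would ordinarily take dose as an input, and tables by dose are routine. The gap is that the handling is not written down.

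A third reply is that the plan claims no power: it is descriptive, and the mismatch comparison is called pilot data. This also stands. The power figures show what the literal wording would cost, not a shortfall against a promise. They rest on a non-transplant SD and model only one of the five contrasts. At log SD 0.70 the loss is 15 points (36% to 21%), not 60.

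**Conclusion.** The point holds as a minor one. The tested variable in 12.2 does not match objective 1, and section 12 is silent on a four-fold dose difference that bears on levels, Cmax and AUC.

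If unadjusted levels were tested over both doses, power for a 1.5-fold autologous/allogeneic difference would fall from about 91% to about 31%. This assumes dose proportionality, log SD 0.34, two-sided 0.05, the log scale, and dose falling at random across groups. The range over assumed SDs is 99% to 33% (SD 0.25) through 36% to 21% (SD 0.70).

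Three stronger readings are not supported.
- **Inflated false positives.** On average the rate stays at about 5%. It rises only at uneven splits in either direction, and the documents do not give the actual split.
- **Harm to the half-life endpoint or half-life comparisons.** None is expected if PK is dose-proportional.
- **Half-life certainly unaffected.** This is also too strong, because proportionality is an expectation and section 7 reports no PK data at 2,000 mg.

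**What to change.** 1. In 12.2, name half-life as the tested variable, to match objective 1, or fold-change from a named post-infusion, pre-transplant sample. Under proportionality no dose term is then needed. If levels, Cmax or AUC are also compared between groups, dose-normalise them or include dose as a term, and state the scale.
2. In 12.1.1, report levels over time, Cmax and AUC by dose (n = 20 and n = 30) or dose-normalised, and name the reference sample for the fold-change.
3. Show half-life by dose before combining it, as a check on proportionality.

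The cost is wording, a few summary tables, and at most one degree of freedom if a dose term is used. No new data are needed. Settling this before the 2,000 mg results are seen avoids a choice guided by the data.

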**Biomarker Assessments:** Immediately prior to mAb administration and at the end-of-infusion, weekly up to week 4, monthly up to week 12, and at week 24 after mAb administration, blood will be drawn by venipuncture (10-20 mL per blood draw) by nursing, a phlebotomist, or trained study staff. At week 12, and monthly thereafter to the end of primary end-point (week 24), blood is self-collected using a TASSO device and by venous blood draw. Nasal specimens will be collected by mid-nasal foam swab at the same time-points as blood draws. Nasal swabs and blood via TASSO (or venous blood draw) will also be collected off-schedule for SARS-CoV-2 PCR and antibody testing as needed based on respiratory symptoms (answering yes to one or more of the nose or chest symptoms) within 48 hours of symptom of symptom onset, up to week 36. If positive for SARS-CoV-2, weekly nasal swabs will be obtained longitudinally for SARS-CoV-2 PCR until negative or until week 36. Serum, plasma, or nasal swabs will be processed and stored at either 4°C, at -20°C, or at -70°C until use, as appropriate. Testing will include serum and nasal total IgG, VIR-7831, SARS-CoV-2-specific IgG, SARS-CoV-2 neutralization titers, and anti-drug antibodies. Testing will be performed at the Fred Hutch, UW, or by Vir Biotechnology.

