## 2. STUDY PURPOSE AND RATIONALE

HCT recipients are most vulnerable to infection during the early post-transplant period; however, active immunization against SARS-CoV-2 is thought to be ineffective during this period because all patients continue on immunosuppressive medications to prevent graft-versus-host disease (GVHD) and the immune system is not yet fully reconstituted(18, 19). In addition, most HCT recipients lose their immunity to various pathogens as soon as during the first months after transplant, irrespective of pre-transplant donor or recipient vaccinations. Current guidelines recommend considering vaccination at least three months

after transplant even though efficacy is unknown and may be sub-optimal. Passive immunization with monoclonal antibodies (mAbs) against SARS-CoV-2 administered pre-transplant represents a strategy to reduce the risk of COVID-19 among HCT recipients this the period of vulnerability when vaccination is not recommended or when vaccine responses may be sub-optimal.

This is a prospective, open-label phase 1 clinical trial that will enroll hematopoietic stem cell transplant candidates to receive the mAb VIR-7831 targeting SARS-CoV-2. The primary objective is to assess the pharmacokinetics of this extended half-life mAb post-transplant.

Previous studies have found that the half-life of CMV- and RSV-specific antibodies is 7-10 days in HCT recipients which is significantly less than the 21-day half-life of IgG in healthy adults(20-22). Although the mechanism of this accelerated decay is unclear, one possible explanation is increased antibody loss through graft versus host disease (GVHD)-related gut leakage which may be more common among recipients of mis-matched unrelated donor stem cell transplants. Monoclonal antibodies against SARS-CoV-2 administered pre-transplant represent a strategy to reduce the risk of COVID-19 among HCT recipients. This study will assess the pharmacokinetics of one such monoclonal antibody with regards to half- in the serum in both autologous and allogeneic transplant recipients. As an exploratory analysis, nasal antibodies may also be measured to determine the bioavailability of VIR-7831 in the nose since this is the portal of entry for infection by SARS-CoV-2.

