## 9.2 Infusion Response Assessment

**Bioanalytical PK method:** This assay will be performed by Vir Biotechnology. A validated Electrochemiluminescence (ECL) Immunoassay is used to quantify sotrovimab in human serum samples. AbD34205 mu IgG2a (an anti-LS monoclonal antibody against the Fc region of VIR-7831) is coated onto an MSD High Bind plate (ECL capable). Sotrovimab in standards, QC's, controls and samples is captured onto the coated plate. After thorough washing of the wells to remove the unbound drug, Ruthenylated AbD42688 rFab is added to the wells. The conjugate binds to the captured sotrovimab. Following the incubation of the detection reagent, the plate is washed followed by addition of freshly prepared 1% formaldehyde for fixation and MSD read buffer. The assay plate is then read using an MSD ECL plate reader. Anti-drug antibodies may also be analyzed.

**Neutralization assay:** This assay may be performed at the Fred Hutch as an exploratory analysis using a SARS-CoV-2 pseudotyped virus assay as previously described(29). Briefly, this is a functional test to assess the ability of antibodies to bind and prevent infection of cultured cells with a pseudotyped virus that utilizes the spike protein of SARS-CoV-2 for infection and expressed luciferase. The endpoint neutralization titer of the serum will be determined as the dilution resulting in 50% neutralization ( $ID_{50}$ ).

**Binding antibodies (IgG):** This assay will be conducted at the Fred Hutch. We will use an indirect enzyme-linked immunosorbent assay (ELISA) or Luminex assay for quantification of anti-SARS-CoV-2 spike and nucleoprotein IgG and total IgG as previously described(30). Briefly, 96-well microtiter plates will be coated with recombinant SARS-CoV-2 spike or nucleoprotein or polyclonal goat anti-human IgG. Serum samples will be initially diluted at 1:100 and nasal samples will be diluted 1:10. Diluted specimens will be incubated in duplicate on the plate followed by addition of secondary goat anti-human IgG-horseradish peroxidase (HRP). Optical densities (OD) will be measured with a spectrophotometer. Plates will include a positive control monoclonal antibody against SARS-CoV-2 spike. If available, donor serum may also be analyzed using an ELISA assay for SARS-CoV-2 spike and nucleocapsid protein to ascertain SARS-CoV-2 infection and vaccination status.

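### The planned serum-versus-nasal-swab comparison has no correction for fluid recovered per swab, so it cannot be read as nasal bioavailability; a paired total-IgG ratio would serve better

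*Combined protocol and SAP*

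**What the plan says.** Section 12.2 commits to the comparison: "We will also compare antibody levels from serum collected by venipuncture versus self-collected using a TASSO device and from fluid collected by nasal swabs". Later in the same paragraph a t-test is named for comparisons, without limiting which ones. Section 12.2 adds, as an option, that "we may also calculate the half-life of VIR-7831 and of SARS-CoV-2 neutralizing antibodies in nasal swabs".

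The purpose is in Section 2: "As an exploratory analysis, nasal antibodies may also be measured to determine the bioavailability of VIR-7831 in the nose". Section 3.2 lists the item as "Exploratory: To measure VIR-7831 and SARS-CoV-2 neutralizing antibodies in nasal swabs and SARS-CoV-2 neutralizing antibodies in serum".

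Section 9.1 has participants collect their own mid-nasal foam swabs at the blood-draw time-points. No section gives a swab weight, a recovered volume, an elution volume or a dilution marker. The one dilution figure is in the binding-antibody assay of Section 9.2: "Serum samples will be initially diluted at 1:100 and nasal samples will be diluted 1:10".

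Total IgG is on the test list. The Synopsis (Biomarker Assessments) says: "Testing will include serum and nasal total IgG, VIR-7831, SARS-CoV-2-specific IgG, SARS-CoV-2 neutralization titers, and anti-drug antibodies". Section 9.2 describes an ELISA or Luminex assay for "quantification of anti-SARS-CoV-2 spike and nucleoprotein IgG and total IgG as previously described". No analysis uses total IgG as a denominator.

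**The concern.** The measured nasal level is the product of the drug concentration in nasal fluid and the fraction of the eluate that is nasal fluid. The second factor is unknown and differs from swab to swab. Serum has no such factor, so a raw nasal:serum contrast mixes penetration into the nose with swab yield. A t-test between the two matrices would show only that they are on different scales.

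The two adjustments in the plan do not help. Normalising to each subject's pre-transplant level (Section 12.1.1) leaves swab-to-swab yield in place. The week 12 correction factor (Section 12.2) is for TASSO against venous blood.

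What is at stake is the exploratory question of whether the antibody reaches the nose. Sections 1 and 2 give it some weight: the LS modification is described as possibly improving respiratory mucosal distribution, and the nose is named as the portal of entry. The assays needed for a better measure are already on the test list.

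**Working it through.** **The plan's own figure.** Section 12.3 counts 4 x 50 = 200 specimens per group for the venous, TASSO and nasal comparison in the first month. The product is right. It counts repeated specimens from 50 people, and TASSO collection starts only at week 12 (Synopsis, Sections 4.1 and 9.1). No SD, effect size, alpha or power is given for the nasal comparison, so there is nothing further to reproduce.

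**Assumptions.** The documents give no recovery or assay variability. I assume a recovery log-SD of 0.5 (0.8 as a worse case), an assay log-SD of a = 0.15 to 0.25, independent assay errors, and nasal samples on days 7, 14, 21, 28, 56, 84, 112, 140 and 168. The half-life examples are 58 days (the preliminary human figure in Section 1 for another antibody, VIR-2482) and 90 days (the up to 3 months in Section 12.3).

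**1. Level.** Observed ratio = true ratio x recovery factor. For an illustrative true ratio of 0.25:
- 5-fold dilution: 0.25 / 5 = 0.05
- 10-fold: 0.25 / 10 = 0.025
- 50-fold: 0.25 / 50 = 0.005

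This is bias, so more participants do not reduce it.

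**2. Decay, recovery unrelated to time.** On the log scale, observed = true + log(recovery). A constant adds only to the intercept. Random recovery adds scatter: in 20,000 simulated series per setting, with a true 58 days and log-SDs of 0.2 to 1.0, the mean slope returned 57.7-58.0 days. The cost is precision:
- Mean day 70, Sxx = 27,930, sqrt(Sxx) = 167.1; slope SE = SD / 167.1.
- 58 days: k = ln2 / 58 = 0.01195. At SD 0.5, 1.96 x SE = 0.00586, so the individual 95% range is ln2 / 0.01781 to ln2 / 0.00609 = 39-114 days. At SD 0.8 it is 32-270 days.
- 90 days: k = 0.00770. At SD 0.5 the range is 51-377 days; at SD 0.8 it has no upper bound.
- Mean slope of 50 people, recovery noise only (SE / sqrt(50)): 54.2-62.3 days for a true 58 at SD 0.5; 76.8-108.7 days for a true 90 at SD 0.8.

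**3. Decay, recovery drifting.** If recovery changes steadily by a factor f over 168 days, ln2 / T_apparent = ln2 / T - ln(f) / 168, where ln2 / 168 = 0.00413.
- 58 days: reads as ln2 / (0.01195 + 0.00413) = 43.1 days if recovery halves, and 88.6 days if it doubles.
- 90 days: reads as 58.6 or 193.8 days.

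Without a yield marker such drift could not be seen.

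**4. Why the IgG denominator must be paired with serum.** VIR-7831 / IgG in the same eluate cancels swab volume. If total IgG itself halves or doubles over 24 weeks, however, 58 days reads as 88.6 or 43.1 days on that scale. Multiplying by same-visit serum IgG removes any change common to serum and nose.

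**5. What the correction does to noise.** Nasal VIR-7831 x (serum IgG / nasal IgG) carries three assay errors, so its log-SD is sqrt(3) x a = 0.26 to 0.43. The uncorrected value carries recovery plus one assay error: sqrt(0.5^2 + a^2) = 0.52 to 0.56. Individual ranges for 58 days:
- a = 0.15: 38-118 days uncorrected, 46-78 corrected
- a = 0.25: 37-129 days uncorrected, 41-100 corrected

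**The case against.** The strongest reply is that this is optional work on an exploratory objective in a descriptive phase 1 study. Section 2 says nasal antibodies may be measured, Section 9.1 keeps swabs only potentially for antibody testing, and Section 12.2 says a nasal half-life may be calculated. That the values would be analysed raw is inferred from silence, and so is applying the general t-test sentence to nasal against serum. Some methods are deferred to cited sources that are not part of the documents. All of this stands, and it limits the importance of the point. It does not supply a correction, and Section 12.2 states the comparison itself without a condition.

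A second reply is that the double ratio is not an absolute nasal:serum ratio. That also stands. Moreover, VIR-7831 is an IgG1 and the total-IgG assay uses a polyclonal anti-human IgG reagent, so the denominator probably includes the drug. If the drug is a share p of serum IgG and its true enrichment over other IgG is E, the double ratio reads E / (1 - p + pE), which is pulled towards 1.

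Three stronger readings are tempting:
- **Nasal decay cannot be read at all.** Constant recovery cancels and random recovery does not bias the slope; the group mean stays usable.
- **The dose rationale is undermined.** Section 1 uses assumed lung:serum ratios, and no section says that nasal swabs would test or replace them.
- **The laboratory dilution is part of the problem.** The 1:10 step is fixed and known, so it can be reversed.

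**Conclusion.** The concern holds for the level comparison: with no correction for swab recovery, the raw serum-versus-nasal contrast cannot answer the bioavailability question in Section 2. The error equals the dilution factor, which the documents do not give; 5- to 50-fold is an assumption.

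For the optional nasal half-life it holds only in part. Individual estimates would be imprecise (39-114 days for a true 58 at log-SD 0.5), and drift in recovery would bias the result unseen (43.1 or 88.6 days for a halving or doubling over 24 weeks). The 50-person mean survives random recovery noise.

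These sizes rest on assumed SDs, drift factors and sampling days. The precision gained by the correction is clear if the assays are tight and modest if they are not; the firmer gains are removing swab volume from the level comparison and making drift in recovery visible. The primary serum half-life is unaffected. This is a worthwhile improvement to an exploratory analysis, not a flaw in the trial's main result.

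**What to change.** In Section 12.2, replace the raw serum-versus-nasal t-test with the same-visit double ratio (nasal VIR-7831 / nasal total IgG) / (serum VIR-7831 / serum total IgG). Report its geometric mean with 95% CI by visit, and describe it as penetration relative to total IgG, not an absolute nasal concentration.

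If a nasal half-life is calculated, fit it to nasal VIR-7831 x (serum IgG / nasal IgG) and show the uncorrected fit as a sensitivity analysis. A gap between the two would point to drift in recovery or a change in IgG partitioning.

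The cost is a derived variable from assays on the existing test list, with no new visits or samples. It has these limits:
- It assumes IgG partitions stably between serum and nose. IVIG is permitted (Section 5.1), and pairing cancels its effect only as far as the nose follows serum.
- Total IgG probably includes the drug, which should be stated with the result.
- Visits with missing IgG drop out.
- It depends on the conditional nasal antibody testing being done. Section 9.2 describes the VIR-7831 assay for serum only, so a method for nasal eluate must be stated as well.
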